11.3.3 Bleeding Days

The numbers of bleeding days by intensity categories (Section 7.6.2) will be calculated for each 28-day interval starting at Study Day 1 up to Study Day 168 in the Treatment Period (i.e., Study Days 1 - 28, Study Days 29 - 56, Study Days 57 - 84, Study Days 85 - 112, Study Days 113 - 140, and Study Days 141 - 168) and the first 28-day interval in the Post-Treatment Follow-up Period (i.e., Study End Days 1 - 28) for each analysis group. For each 28-day interval, each analysis includes subjects who did not premature discontinue in or before this 28-day interval. For example, for Study Days 29 - 56, it includes subjects who were on treatment for at least 56 days in the extension study. For Final Month analysis, it includes subjects who were on treatment for at least 38 days in the extension study. The summary of average number of bleeding days in a 28 day window during the Treatment Period will be provided for each analysis group by intensity categories.

If a subject did not have evaluable AH data during an interval and no bleeding was indicated on UBQ ("Subject only has spotting that did not require the use of sanitary products" or "There was no visible blood on the sanitary products" was allowed), then the number of bleeding days over the interval is 0. The number and percentage for each analysis group and overall will be provided for subjects who did not have evaluable AH data during an interval and bleeding was indicated on UBQ.

The change and percent change from Baseline in the numbers of bleeding/spotting days and bleeding days to each 28-day interval and Final Month in the Treatment Period and the first 28-day interval in the Post-Treatment Follow-up Period will be summarized for each analysis group, respectively.

11.3.4 Hemoglobin Concentration

Hemoglobin (Hgb) concentration data will be summarized as observed.

The change and percent change from Baseline in Hgb concentration to Months 1-6 during the Treatment Period will be summarized by analysis group.

The number and percentage of subjects with changes in Hgb concentration from Baseline to Months 1 - 6 during the Treatment Period in each of the following categories will be summarized by analysis group.

- Change from Baseline in Hgb ≤ -1.0 g/dL
- $-1.0 \text{ g/dL} < \text{Change from Baseline in Hgb} \le -0.5 \text{ g/dL}$
- -0.5 g/dL < Change from Baseline in Hgb < 0.5 g/dL
- 0.5 g/dL \leq Change from Baseline in Hgb < 1.0 g/dL
- $1.0 \text{ g/dL} \leq \text{Change from Baseline in Hgb} < 1.5 \text{ g/dL}$
- 1.5 g/dL \leq Change from Baseline in Hgb < 2.0 g/dL
- Change from Baseline in Hgb ≥ 2.0 g/dL

Also, shift tables from Baseline to Month 3 and Month 6 will be summarized by the following categories.

- Hgb ≤ 10.5 g/dL
- $10.5 \text{ g/dL} < \text{Hgb} \le 12 \text{ g/dL}$
- Hgb > 12 g/dL

The number and percentage of subjects who had Hgb Baseline ≤ 10.5 g/dL and have an increase in Hgb concentration > 2 g/dL from Baseline will be summarized for each month by analysis group.

The number and percentage of subjects who had Hgb Baseline ≤ 10.5 g/dL and have an increase in Hgb concentration > 1 g/dL from Baseline will be summarized for each month by analysis group.

In addition, the number and percentage of subjects who have an increase in Hgb concentration > 1 g/dL from Baseline will be summarized for each month by analysis group and Baseline Hgb concentration categories as follows. Same summary will be provided for increase in Hgb concentration > 2 g/dL from Baseline to each month.

- Hgb ≤ 10.5 g/dL
- $10.5 \text{ g/dL} < \text{Hgb} \le 12 \text{ g/dL}$
- Hgb > 12 g/dL

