### **5.4 Removal of Subjects from Therapy or Assessment**

Each subject has the right to withdraw from the study at any time. In addition, the Investigator may discontinue a subject from the study at any time if the Investigator considers it necessary for any reason, including the occurrence of an adverse event or noncompliance with the protocol. Subjects who withdraw from the study will not be replaced. Each subject will be withdrawn from the study if any of the following occur:

- The subject decides to withdraw consent for any reason.
- The investigator believes it is in the best interest of the subject.
- Clinically significant deterioration of the subject's medical status as determined by the investigator.
- The subject requires surgical intervention for treatment of uterine fibroids and menstrual bleeding or other procedures including hysterectomy, myomectomy, uterine artery embolization, high intensity focused ultrasound (HIFU), endometrial ablation, dilation and curettage (D&C), etc. during the Treatment Period. In the post treatment period these procedures do not warrant withdrawal if performed during the Post-Treatment Period unless a hysterectomy with bilateral salpingo-oophorectomy (BSO) is performed and the Subject does not plan to use Hormone Replacement Therapy within 1 month of the surgery date.
- The subject becomes pregnant.

- The subject has ALT or AST elevation > 5 times the upper limit of normal confirmed upon repeat during the Treatment Period.
- The subject's legally acceptable representative decides to withdraw consent for any reason (when applicable).
- Heavy menstrual bleeding during the Treatment Period that requires a blood transfusion at any time after having taken 28 days of study drug. If a subject has a blood transfusion during the Post-Treatment Period, the AbbVie TA MD should be contacted to determine if the subject can remain in the study.
- Any other medical reason that AbbVie or the study investigator deems appropriate.

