#### **5.4.1 Discontinuation of Individual Subjects**

In the event that a subject withdraws or is prematurely discontinued from study drug treatment, the subject should complete the Treatment Period Premature Discontinuation Visit as soon as possible (preferably within 2 days of last dose of study drug, if possible) and undergo study procedures as outlined in [Appendix C](#), Study Activities. Subjects who prematurely discontinue during the Treatment Period are expected to enter the 12-Month Post-Treatment Follow-Up Period, unless discontinuing due to pregnancy. Each subsequent monthly Post-Treatment Follow-Up Period Visit should be scheduled based on the date of the last dose of study drug.

In the event that a subject withdraws or is prematurely discontinued during the Post-Treatment Follow-Up Period, the subject should complete the Post-Treatment Premature Discontinuation Visit as soon as possible and undergo study procedures as outlined in [Appendix C](#), Study Activities. These procedures should not interfere with the initiation of any new treatments or therapeutic modalities the Investigator determines are necessary to treat the subject's condition. The reason(s) for the discontinuation from the study will be recorded in the eCRFs.

All used and unused study drug containers will be returned to the study site.

If a subject becomes pregnant during the Treatment or Post-Treatment Follow-Up Periods, no additional study procedures, except an ultrasound will be conducted. Refer to Section 6.1.6 for instructions on reporting of a pregnancy to the Sponsor and the required follow-up on the subject/fetus and live births.

If a subject is discontinued from the study with an ongoing adverse event or an unresolved laboratory result that is clinically significant (as determined by the Investigator), the Investigator will attempt to provide follow-up until a satisfactory clinical resolution of the laboratory result or adverse event is achieved.

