**Appendix C. Study Activities – Treatment Period and Post-Treatment Follow-Up Period**

**Treatment Period**

Procedure	Day 1 b	Treatment Period a						Unsch Visit	PD (if appl)
		Month 1	Month 2	Month 3	Month 4	Month 5	Month 6		
Informed Consent	X d								
Gynecological (External Genitalia, Pelvic and Breast) Examination						X			X
Pap Test						X			X
Endometrial Biopsy						X e			X e,f
Complete Physical Examination Including Weight						X			X
Symptom-Directed Physical Examination		X	X	X	X				
Vital Signs (Temp, BP, Pulse, RR)		X	X	X	X			X	X
12-Lead Electrocardiogram (ECG)									X
Mammogram									X g
Pelvic Ultrasound: TAU, TVU				X h					X h,i
MRI (Subset of Subjects)									X h,j
DXA Scan			X k						X l
Dispense Sanitary Products and Collection Kit (Keg, Collection Bags, etc.) as Needed	X	X	X	X	X		X	X	X
Collect and Return Sanitary Products and Draw Venous Blood Sample		X l	X l	X l	X l		X l	X	X

Procedure	Treatment Period a										PD (if appl)	
	Day 1 b	Month 1	Month 2	Month 3	Month 4	Month 5	Month 6	PCV c	Unsch Visit			
UBQ		X m	X m	X m	X m	X m	X m	X m	X m	X m	X m	X m
Clinical Safety Labs: Chemistry, Lipid Panel and Hematology		X	X	X	X	X	X					X
Clinical Safety Labs: Chemistry Creatinine Phosphokinase						X	X					X
Clinical Safety Labs: Urinalysis				X	X	X	X					X
Apolipoprotein A and B				X	X	X	X					X
Endocrine: FSH and LH		X	X	X	X	X	X					X
Endocrine: Reflexive TSH and Thyroxine-Binding Globulin (TBG)				X			X n					X n
Pharmacodynamic Sample: Serum Estradiol (E2) and Progesterone (P)		X	X	X	X	X	X					X
Pharmacokinetic Sample (PK): Elagolix and NETA Plasma Concentration		X	X	X	X	X	X					X
Urine Pregnancy Tests	X o	X p,q	X p,q	X p,q	X p,q	X p,q	X q	X				X
Serum Pregnancy Tests							X					X
Contraception Counseling/Dispense Contraceptives as Necessary	X f	X	X	X	X	X	X	X				X
Birth Control Attestation	X						X					X

Procedure	Treatment Period a										PD (if appl)	
	Day 1 b	Month 1	Month 2	Month 3	Month 4	Month 5	Month 6	PCV c	Unsch Visit			
PRO Questionnaires							X				X	X

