5.0 Analysis Populations

5.1 Definition for Analysis Populations

Full Analysis Set

The full analysis set is comprised of all randomized subjects who have received at least one dose of study drug in this study. The data from the full analysis set will be presented by the treatment group assigned at the time of randomization, even if the subject does not receive the correct treatment or does not follow the protocol until completion. The full analysis set will be used for all Baseline and efficacy analyses.

Safety Analysis Set

The Safety Analysis Set will include all randomized subjects who received at least one dose of study drug. The data from the safety analysis set will be presented by the treatment group as treated, independent of treatment group assignment at the time of randomization. If a subject receives more than one treatment, she will be analyzed in the treatment group to which she was randomized. The safety analysis set will be used for all safety analyses.

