7.4 Definition of Analysis Window

7.4.1 Treatment Period

Data obtained more than 3 days after the subject's last dose of study drug in the extension study will be excluded for assessments in the Treatment Period with the following exceptions:

- 1. For BMD, TVU/TAU, MRI, and endometrial biopsy assessments, data obtained more than 28 days after the last dose of study drug in the extension study will be excluded from summaries/analyses in the Treatment Period.
- 2. For Alkaline Hematin (AH) data, data obtained after the last dose of study drug in the extension study will be excluded from the summaries/analyses in the Treatment Period.

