11.3 Secondary and Other Efficacy Analyses

Secondary efficacy endpoints during the Treatment Period include the following:

- Change and percent change from Baseline in MBL volume to each month and to the Final Month;
- Percentage of subjects with suppression of bleeding (no bleeding allowed, spotting allowed) at the Final Month;
- Percentage of subjects with Baseline hemoglobin ≤ 10.5 g/dL who have an increase in hemoglobin > 2 g/dL at Month 6.

Other efficacy endpoints during the Treatment Period include the following:

- Percentage of subjects with MBL volume < 80 mL and 50% or greater reduction in MBL volume from Baseline during 28-day intervals throughout the Treatment Period;
- Percentage of subjects with amenorrhea;
- Percentage of subjects with control of bleeding;
- The number of bleeding days;
- Change and percent change from Baseline in hemoglobin concentration;
- Patient Global Impression of Change (PGIC) questionnaire for Menstrual Bleeding and Non-Bleeding Uterine Fibroid Symptoms;

- Change and percent change from baseline in fibroid and uterine volume;
- Change from baseline for the UFS-QoL;
- Change from baseline for the EuroQoL-5D (EQ-5D-5L);
- The Health Care Resource Utilization (HCRU) questionnaire;
- Change from baseline for the WPAI.

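### The Month 6 hemoglobin response rate has no rule for women who stop drug before Study Day 152, so it probably describes only those who stayed about five months

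*SAP*

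**What the plan says.** SAP 11.3 lists three secondary endpoints. The third is "Percentage of subjects with Baseline hemoglobin ≤ 10.5 g/dL who have an increase in hemoglobin > 2 g/dL at Month 6". The analysis section, SAP 11.3.4, states that "Hemoglobin (Hgb) concentration data will be summarized as observed". It gives the rate for each month by analysis group. It has no rule for women without a value, no summary at the Final Visit and no stated denominator for the percentage.

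Three other parts of the plan decide who can have a Month 6 value:

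- SAP Table 1 (monthly measurements) sets Month 6 as Study Days above 154 and up to 196, with nominal day 168.
- SAP 7.4.1 says of the Treatment Period: "Data obtained more than 3 days after the subject's last dose of study drug in the extension study will be excluded". Hemoglobin is not among the listed exceptions.
- Protocol Appendix C schedules "Clinical Safety Labs: Chemistry, Lipid Panel and Hematology" at Months 1 to 6 and at the Premature Discontinuation Visit. Protocol 5.4.1 places that visit "preferably within 2 days of last dose of study drug, if possible".

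On the analysis set, SAP 5.1 says: "The full analysis set will be used for all Baseline and efficacy analyses". For the primary endpoint, SAP 11.2.1 scores a woman as a non-responder if her primary reason for stopping study drug is lack of efficacy, need for fibroid surgery or invasive intervention, or an adverse event, whatever her blood loss.

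**The concern.** A woman who stops early can count as a failure on the primary endpoint and be absent from the hemoglobin endpoint. Some reasons for stopping, such as lack of efficacy or surgery for fibroids and bleeding, are plausibly linked to poor hemoglobin recovery. If these women drop out of both numerator and denominator, the rate describes only those who stayed on drug for about five 28-day months. A reader who knows that efficacy is analysed in the full analysis set would take it as the rate among all treated women who were anemic at baseline.

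The plan covers early stoppers elsewhere. The other two secondary endpoints, change in menstrual blood loss and suppression of bleeding, are given at the Final Month. Amenorrhea has a carried-forward version (SAP 11.3.2.1). The questionnaires in SAP 11.3.6.1 to 11.3.6.5 have Final Visit summaries. Hemoglobin response is the only secondary endpoint whose sole specified time point is a fixed visit. The missing rule therefore looks like a gap rather than a decision.

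**Working it through.** **1. The window reproduces.** The lower edge is the midpoint of nominal Days 140 and 168: (140 + 168)/2 = 154. The upper edge is 168 + 28 = 196. Both match SAP Table 1, so the first eligible day is 155.

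**2. Last dose needed for a Month 6 value.** With last dose on Day L, the latest usable sample is on Day L + 3. The condition L + 3 ≥ 155 gives L ≥ 152.

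| Last dose (Study Day) | Latest usable sample | Inside Month 6 window? |
|---|---|---|
| 151 | 154 | No |
| 152 | 155 | Yes |
| 153 | 156 | Yes |
| 154 | 157 | Yes |

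A last dose on Day 151 or earlier rules out a Month 6 value. In 28-day months, 152/28 = 5.4.

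**3. The discontinuation sample exists but is filed elsewhere.** A visit within 2 days of the last dose is inside the 3-day allowance, so the sample counts as Treatment Period data. Table 1 then assigns it to its own month. For example, a last dose on Day 100 and a sample on Day 102 fall in Month 4 (above 98, up to 126). The sample never reaches the Month 6 rate.

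**4. Size of the difference.** Let d be the share of women with baseline hemoglobin of 10.5 g/dL or less who have no Month 6 value, p the observed-case rate, and q the rate among those missing.

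- Rate over all such women: (1 − d)p + dq.
- Observed-case rate minus that rate: p − (1 − d)p − dq = d(p − q).

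The documents give no d, p or q, so every value below is an assumption.

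*All missing women scored as failures (q = 0): the difference is p × d.*

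| p | d | Full-set rate p(1 − d) | Difference |
|---|---|---|---|
| 50% | 5% | 47.5% | 2.5 points |
| 50% | 10% | 45% | 5 points |
| 50% | 20% | 40% | 10 points |
| 50% | 25% | 37.5% | 12.5 points |
| 50% | 30% | 35% | 15 points |

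Over p = 30% to 70% and d = 5% to 30%, the range is 0.30 × 0.05 = 1.5 points to 0.70 × 0.30 = 21 points.

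*Other values of q.* If q = p, the difference is 0. If q is 20 points above p, the observed-case rate is too low by 0.20 × d, which is 1 to 6 points for d = 5% to 30%.

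*In counts.* Take 100 women, 20 without a Month 6 value and 40 responders among the other 80. The observed-case rate is 40/80 = 50%. If 0, 5, 10, 15 or 20 of the 20 had responded, the rate over all 100 is 40%, 45%, 50%, 55% or 60%.

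**5. Size under the proposed scoring.** The fix below does not score every missing woman as a failure. Split d into d1 (stopped for one of the three SAP 11.2.1 reasons, scored as failures) and d2 (the rest, scored on their last on-treatment value, with rate q2). The difference is d1 × p + d2(p − q2). With p = 50%, d = 20% split equally and q2 = 50%, it is 0.10 × 50 + 0 = 5 points, against 10 if all were failures. So p × d is an upper limit for the effect of the fix when q2 is above 0.

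**The case against.** The strongest reply is that this is an ordinary observed-case summary by visit in a descriptive study. The full analysis set defines who is eligible, and the SAP restricts by time on drug elsewhere: monthly blood loss leaves out women who stopped in or before the interval (SAP 11.3.1), and suppression of bleeding needs at least 38 days on drug (SAP 11.3.2.2). Final on-treatment hemoglobin is already shown, in shift tables and final-against-baseline plots (SAP 12.3.1), and reasons for stopping are tabulated (SAP 9.0). All of this is true, and it lowers the stakes. None of it gives the rate of a rise above 2 g/dL with early stoppers included, or says how they are counted.

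A reader might also infer more than the documents support:

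- **That the plan expressly removes these women.** It does not. SAP 11.1 requires both values for visit means, but says nothing of percentages, and SAP 5.1 allows the opposite reading. Two programmers could report different rates.
- **That the cut-off is Day 155.** This overlooks the 3-day allowance.
- **That the rate must be too high.** A BMD decrease of 8% or more at Month 3 ends treatment (Protocol 5.3.1.1), and the adverse events that most often led to discontinuation across elagolix studies were hot flush, headache and nausea (Protocol 3.2.2). Such women may already have had the hemoglobin rise. Scoring them as failures is a choice of estimand in line with the primary endpoint, not the correction of a proven bias.
- **That early transfusion inflates the rate.** Protocol 5.4 withdraws a woman whose heavy bleeding on treatment "requires a blood transfusion at any time after having taken 28 days of study drug", so an earlier one need not end participation. But Day 28 is 155 − 28 = 127 days before the window opens, nothing in the documents shows an effect lasting that long, and the text does not say whether the 28 days restart in the Extension.
- **That the Month 6 fibroid and uterine volume reductions share the fault.** Their rules differ: imaging counts up to 28 days after last dose and Month 6 starts on Day 141, so a last dose on Day 141 − 28 = 113 can still give a value.

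**Conclusion.** The point holds as a gap in specification with a probable direction. A woman whose last dose is before Day 152 cannot contribute to the Month 6 hemoglobin endpoint, SAP 11.3.4 does not say how she is counted, and the natural reading drops her even where the primary endpoint calls her a failure. The resulting rate is likely to exceed the full-set rate, but this depends on q being below p, which the documents cannot settle. The illustrative 5 to 12.5 points rests on assumed values (p = 50%, d = 10% to 25%) and on scoring every missing woman as a failure. Efficacy is descriptive, so no test, type I error or power is affected. It is a cheap improvement worth making to a named secondary endpoint.

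**What to change.** In SAP 11.3.4:

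1. Set the denominator to all full-analysis-set women with baseline hemoglobin of 10.5 g/dL or less.
2. Score as non-responders those without a Month 6 value whose primary discontinuation reason is an adverse event, lack of efficacy or fibroid surgery or intervention, as in SAP 11.2.1.
3. For women missing a Month 6 value for any other reason, use the last on-treatment hemoglobin (Final Visit, SAP 7.2). State how a woman with no on-treatment value at all is scored.
4. Add the rate of a rise above 2 g/dL at the Final Visit. This shows women who stopped for an adverse event after their hemoglobin had already recovered.
5. Report the number without a Month 6 value per analysis group, and keep the observed-case rate as a sensitivity analysis.

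The cost is SAP wording and one extra table from samples already scheduled. The reported rate may become slightly less favourable.

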11.3.5 Fibroid and Uterine Volume, FIGO Classification, Adenomyosis, and Post-Treatment Menses

11.3.5.1 **Fibroid and Uterine Volume**

Fibroid and uterine volume data will be summarized as observed. Analyses will be conducted separately for results obtained from TAU/TVU and MRI.

The change and percent change in the volume of the largest (primary) fibroid, the total fibroid volume (3 largest fibroids), and the uterine volume from Baseline to Month 3 (if applicable) and Month 6 during the Treatment Period will be summarized for each analysis group. The change and percent change at Post-Treatment Month 3 and Post-Treatment Month 6 (if applicable) during the Post-Treatment Follow-up Period will also be summarized for each analysis group.

The number and percentage of subjects with $\geq 25\%$ reduction from Baseline in total fibroid volume at Month 3 (if applicable) and Month 6 each during the Treatment Period will be summarized for each analysis group. The same summary will be provided for largest (primary) fibroid volume and uterine volume, respectively.

FIGO Classification 11.3.5.2

The number and percentage of subjects with fibroids at each location (e.g., intramural, subserosal, submucosal non-pedunculated, and subserosal pedunculated) according to the FIGO classification³ will be summarized for each analysis group at Baseline, Month 3 (if

applicable) and Month 6 during the Treatment Period and Post-Treatment Month 3 and Post-Treatment Month 6 (if applicable) during the Post-Treatment Follow-up Period.

